10.9 Pregnancy Reporting

Pregnancy is an exclusion for participation and pregnancy does not need to be reported if it is discovered before taking any dose of the study drug. However if a participant becomes pregnant between discharge from hospitalisation and the 90-day follow-up period this should be recorded and reported with a view to obtaining outcome of the pregnancy.

The investigator must report the pregnancy within 24hours of being notified of it by emailing the "Clinical Trial Pregnancy Form: Initial Report" to [contact] (or faxing if email not possible on [name]). PRODUCTLIFE will inform the Sponsor of the pregnancy within 1 working day of receiving notification. The investigator must diligently follow the participant until delivery or termination of pregnancy, providing necessary updated information to PRODUCTLIFE using the 'Clinical Trial Pregnancy Form: Follow-up Report'.

Information on the status of the mother and child after delivery will be forwarded to PRODUCTLIFE using the 'Pregnancy Outcome;' section of the 'Clinical Trial Pregnancy Form: Follow-up Report'. Generally follow up will occur within 6 to 8 weeks following the estimated delivery date. Any premature termination of the pregnancy will also be reported on this form.

Although pregnancy occurring in a clinical study is not considered to be an AE or SAE, any pregnancy complication or elective termination of a pregnancy for medical reasons will be recorded

as an AE or SAE and will be followed up as such. A spontaneous abortion is always considered to be an SAE and should be recorded and reported to PRODUCTLIFE as such.

10.10 Independent Safety Data Monitoring Committee (SDMC)

An independent safety data monitoring committee (SDMC) will be appointed to review accumulating adverse event data and patient safety. The SDMC will evaluate the safety in relation to PP100-01 dosing step increase. The committee will give recommendations on the continuation or termination of the study by detection of any safety signals as early as possible in accordance with the SDMC Charter.

Proposed composition of SDMC will be: Chairperson, Hepatologist, Statistician, Independent Clinical Pharmacologist/Toxicologist.

During the period of recruitment into the study, interim analyses of in-hospital mortality/morbidity and of any other information that is available on major outcome events (including serious adverse events believed to be due to treatment) will be supplied, in strict confidence, to the Chairperson of the SDMC, along with any other analyses that the committee may request.

All further patient enrolment will be paused pending advise from the SDMC if one of the following stopping rules have been met: 1. Patient death, admission to a Critical Care Unit or admission to a Liver Transplantation Unit due to any reason, or 2. One SUSAR that definitely or probably relates to either PP100-01 or NAC or both.

All SMDC data review will be documented and all meetings will have written minutes, which will be filed in the Trial Master File (TMF) upon completion of the study.

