10.4.2 Assessment of Causality

The Investigator must make an assessment of whether the AE/SAE is likely to be related to treatment according to the following definitions. All AEs/SAEs judged as having a reasonable suspected causal relationship (e.g. possibly, probably, definitely) to the study drug will be considered as ARs/SARs. If concomitant or rescue/escape drugs are given, the Investigator must also make an assessment of whether the AE/SAE is likely to be related to an interaction between the study drug and concomitant or rescue/escape drugs or whether the AE/SAE might be linked to either the study drug or concomitant or rescue/escape drugs but cannot be attributed to only one of these drugs. All AEs/SAEs judged as being related (e.g. possibly, probably, definitely) to an

interaction between the study drug and concomitant or rescue/escape drugs, or any AE/SAE that cannot be attributed to only the study drug or the concomitant or rescue/escape drugs will also be considered to be ARs/SARs.

Unrelated: where an event is not considered to be related to the study drug.

Possibly: although a relationship to the study drug cannot be completely ruled out, the nature of the event, the underlying disease, concomitant medication or temporal relationship make other explanations possible.

Probably: the temporal relationship and absence of a more likely explanation suggest the event could be related to the study drug.

Definitely: The known effects of the study drug or its therapeutic class, or based on challenge testing, suggest that study drug is the most likely cause.

Alternative causes such as natural history of the underlying disease, other risk factors and the temporal relationship of the event to the treatment should be considered and investigated. The blind should not be broken for the purpose of making this assessment.

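### The SUSAR trigger for pausing enrolment omits events graded *possibly* related, although the protocol counts them as suspected reactions

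*Protocol*

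**What the plan says.** Protocol Section 10.10 states the consequence first: "All further patient enrolment will be paused pending advise from the SDMC". Two rules lead to it, and the synopsis repeats them.

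- **Rule 1:** "Patient death, admission to a Critical Care Unit or admission to a Liver Transplantation Unit due to any reason". It needs no causality judgement.
- **Rule 2:** "One SUSAR that definitely or probably relates to either PP100-01 or NAC or both".

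Section 10.4.2 defines the causality grades and says which of them make an event a reaction: "All AEs/SAEs judged as having a reasonable suspected causal relationship (e.g. possibly, probably, definitely) to the study drug will be considered as ARs/SARs". Section 10.2 adds the other elements of a SUSAR. The event must be serious, which includes prolonging an existing hospital stay, and not consistent with the IB or SoPC. Section 10.8 sends SUSARs to authorities and ethics committees within 7 days if fatal or life-threatening, and within 15 days otherwise.

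The routine SDMC review described in the synopsis takes place after each dosing cohort and before the next one opens. Section 6.6.1 sets the cohort at 8 patients, 6 on PP100-01 plus NAC and 2 on NAC alone.

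**The concern.** The protocol uses two causality thresholds. One decides what counts as a suspected reaction and must be reported urgently. The other, which is higher, decides what pauses enrolment. The documents do not explain the difference.

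The omitted grade matters in this population. The definition of *possibly* covers cases where "the nature of the event, the underlying disease, concomitant medication or temporal relationship make other explanations possible". Every patient here has taken an overdose that can itself injure the liver, every patient receives NAC, and SAP Section 4.2 plans to tabulate other drugs ingested. Alternative explanations will often be available.

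Section 12.3 notes that PP100-01 has not been given before to overdose patients treated with NAC, and Section 13.1 calls the risks of the co-treatment unknown. Rule 2 is the only automatic pause that rests on a suspected drug reaction. If it stays silent, recruitment at the same dose can continue on the original schedule.

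**Working it through.** The plan gives no figure for the pause rule, so there is nothing to reproduce. The check is mainly a comparison of texts.

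**Step 1: the two thresholds side by side**, for an event that is serious and unexpected.

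| Causality grade | Suspected reaction (10.4.2) | Expedited report (10.8) | Rule 2 pauses enrolment (10.10, synopsis) |
|---|---|---|---|
| Unrelated | No | No | No |
| Possibly | Yes | Yes | **No** |
| Probably | Yes | Yes | Yes |
| Definitely | Yes | Yes | Yes |

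The *possibly* row is the gap.

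**Step 2: what rule 1 recovers.** It catches any event that ends in death, critical care admission or transplant-unit admission, at any grade. What remains is a SUSAR graded *possibly* that is managed on the ward, or that is serious only because it prolongs the stay.

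**Step 3: an example that falls through.** Suppose serious liver injury after PP100-01 prolongs hospitalisation without critical care or transplant-unit admission. *Probably* requires that "the temporal relationship and absence of a more likely explanation suggest the event could be related to the study drug". Here the overdose is a more likely explanation, so *possibly* is the natural grade. Counting NAC in rule 2 does not help, because the competing cause is paracetamol. Neither rule is met. The example assumes that the event is unexpected per the IB, which is an appendix not available for this review.

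**Step 4: when the grades for the two drugs differ.** SAP Sections 4.4 and 4.9 record relatedness and expectedness separately for NAC and PP100-01. Consider an anaphylactoid-type event that is expected for NAC and *probably* related to it, but unexpected for PP100-01 and only *possibly* related to it. It is a SUSAR for PP100-01 only. Read literally, rule 2 fires, because the event probably relates to one of the two drugs. Read drug by drug, it does not, because no drug has both a SUSAR and a qualifying grade. The protocol does not say which reading applies.

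**Step 5: worst-case exposure.** If the first of the 6 PP100-01 patients in a cohort has such an event, 6 − 1 = 5 planned patients remain at that dose before the end-of-cohort review.

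**Step 6: illustration only.** None of these inputs is in the documents. Let p be the chance of a SUSAR per PP100-01 patient, q the share graded *possibly*, and c the share of those that also meet rule 1. Patients are taken as independent, with at most one SUSAR each.

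- Chance of at least one SUSAR in a cohort of 6: 1 − (1 − p)^6
- Chance of at least one SUSAR that pauses enrolment: 1 − (1 − p[1 − q(1 − c)])^6

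For p = 10%, q = 50%, c = 0: 1 − 0.90^6 = 46.9%, against 1 − 0.95^6 = 26.5%. With c = 50%: 1 − 0.925^6 = 37.4%.

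| p | Any SUSAR | Pause, c = 0 (q = 25 / 50 / 75%) | Pause, c = 50% (q = 25 / 50 / 75%) |
|---|---|---|---|
| 5% | 26.5% | 20.5 / 14.1 / 7.3% | 23.5 / 20.5 / 17.3% |
| 10% | 46.9% | 37.4 / 26.5 / 14.1% | 42.3 / 37.4 / 32.1% |
| 20% | 73.8% | 62.3 / 46.9 / 26.5% | 68.5 / 62.3 / 55.1% |

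For a single SUSAR the chance of no automatic pause is q(1 − c). Over these values it runs from 0.25 × 0.5 = 12.5% to 0.75 × 1 = 75%. The range is wide because q and c are unknown.

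**The case against.** The strongest reply is that reporting and pausing serve different purposes. A sponsor may reasonably report every suspected reaction yet pause only for the better-supported ones, so two thresholds are not in themselves a contradiction. That stands. What remains is that the protocol gives no reason for the choice, and the ambiguity in step 4 exists under either policy.

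The second reply is that other safeguards apply. SAEs are reported within 24 hours (Sections 10.5 and 10.6). Section 6.6.1 leaves 24 hours after the first PP100-01 patient in each cohort. During recruitment the SDMC Chairperson receives information on major outcome events, including SAEs thought due to treatment (Section 10.10). Investigators may end the study at any time (Section 16.5). These are real, and they make the figure of 5 a worst case. However, the 24-hour gap follows only one patient per cohort, no timing is stated for the Chairperson's data, and the rest is discretionary. None is an automatic pause. The SDMC Charter may say more but is not available for this review.

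A reader might also infer more than the documents support:

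- *That most SUSARs would be graded possibly.* No grade distribution is given. *Probably* asks only that no explanation be more likely, not that none exist, and onset minutes after the bolus could support it.
- *That definitely is out of reach for an unexpected event.* Its definition rests on "The known effects of the study drug or its therapeutic class, or based on challenge testing". Class knowledge can be wider than the product information, and Section 2.3 cites about 240,000 patients given the closely related mangafodipir. NAC may also be restarted after an anaphylactoid reaction (Section 9.3).
- *That a suspected serious reaction would go unchecked.* Rule 1 applies whatever the cause, *probably* and *definitely* related SUSARs do pause enrolment, and SDMC review precedes every dose step at any grade. The rule concerns enrolment, not the dosing of patients already enrolled.

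**Conclusion.** The gap is real and narrow. A SUSAR graded *possibly* related, without death, Critical Care Unit admission or Liver Transplantation Unit admission, goes for expedited reporting but does not automatically pause enrolment. Nothing else in the two documents supplies such a pause.

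Its frequency cannot be estimated from the documents, and the table above only shows how strongly it depends on unstated inputs. The worst-case count of 5 further patients rests on three conditions: the event occurs in the cohort's first PP100-01 patient, nobody uses their discretion to intervene, and no patient is added as a replacement under Section 6.7.

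This should be fixed, because it is an unexplained mismatch in a safety rule and costs little to resolve. It does not undermine the study design.

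**What to change.** Reconcile rule 2, in Section 10.10, in the synopsis and in the SDMC Charter, with Section 10.4.2, so that the enrolment-pause trigger and the definition of a suspected reaction use the same causality threshold. If the difference is deliberate, the protocol should at least give the reason.

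In the same edit, state how rule 2 applies when relatedness or expectedness differs between NAC and PP100-01, in line with the separate recording in SAP Sections 4.4 and 4.9.

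The drafting cost is about one sentence in two places, plus the Charter. The operating cost is an occasional extra ad hoc SDMC review and a short enrolment pause, with the SDMC still advising on whether recruitment resumes. How often that would occur depends on the same unknown share of *possibly* graded SUSARs, but it cannot exceed the number of SUSARs in a study planned for 24 patients.

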Anaphylactoid reactions, characterised by symptoms such as rash, wheeze, and hypotension are thought to be dose and rate-related. Studies in Edinburgh have demonstrated that these are mediated by histamine release (Pakravan et al 2008). In one prospective randomised controlled study, the rate of anaphylactoid reactions was 18% (Kerr et al 2005). A recent prospective study of patients treated with the standard intravenous NAC regimen in the Edinburgh toxicology unit showed that around 15% developed anaphylactoid reactions (Pakravan 2008) and similar figures have been reported from Newcastle (Fathalla et al 2008). Anaphylactoid reactions are managed by interrupting the infusion temporarily and administering an antihistamine and bronchodilators. Most affected patients can be restarted on NAC at a lower infusion rate. Females, asthmatics and patients with low plasma APAP concentrations are at higher risk of anaphylactoid reactions (Schmidt et al 2001, Waring et al 2006, Pakravan 2008) and fatal adverse reactions have been reported, although these are rare.

Although highly effective, especially if started within a few hours of paracetamol overdose, the current licensed intravenous 20.25hr NAC regimen has several disadvantages. Firstly, intravenous NAC is commonly associated with adverse effects, the most common being nausea, vomiting and anaphylactoid reactions. Anaphylactoid reactions appear related to the rate of infusion of NAC and its concentration in blood. Thus they are most common during, or soon after, the initial high dose infusion. Secondly, the infusion schedule is complex, requiring prescription of three different infusions, and this contributes to a high risk of medication errors, which may have serious, potentially life-threatening, adverse outcomes. Thirdly, the required duration of the infusion regimen results in prolonged hospital stay, especially as patients with paracetamol overdose often present during the night (Thanacoody et al 2013).

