Calmangafodipir (PledOx[®]) had a safety profile in this study as would be predicted by non-clinical data. The most common preferred terms for safety reporting in the study (more than 25 events reported in total) were: neurotoxicity, thrombocytopenia, fatigue, nausea, neutropenia, peripheral sensory neuropathy, diarrhea, leukopenia, decreased appetite, anemia, paresthesia, neuropathy peripheral, vomiting and pyrexia. As expected, the frequencies of neurotoxicity, thrombocytopenia and neutropenia that were reported as AEs mirrored the reporting of these symptoms as chemotherapy-induced toxicities analyzed as efficacy data. Grade 2 neurotoxicity occurred in a smaller proportion of patients in the 5 μ mol/kg PledOx[®] group (4.4%, 2 events) compared to placebo (16.7%, 16 events). No other apparent differences between the treatment groups in terms of adverse events.

To date, approximately 150 patients with mCRC received repetitive dosing with calmangafodipir (PledOx[®]). Approximately 240,000 patients have received single doses of the closely related compound mangafodipir at similar or higher doses. No new significant safety data have emerged during the treatment reporting period. Immediate blood pressure fall, severe diarrhoea and severe vomiting, have previously been identified as important potential risks, to be closely monitored as the clinical program progresses.

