10.2 Definitions

An **adverse event** (AE) is any untoward medical occurrence in a clinical study patient who is administered a medicinal product, which does not necessarily have a causal relationship with the treatment.

An **adverse reaction** (AR) is any untoward or unintended response to an investigational medicinal product related to any dose administered.

An **unexpected adverse reaction** (UAR) is an adverse reaction that is not consistent with the product information in the IB/SoPC.

A serious adverse event (SAE), serious adverse reaction (SAR) or suspected unexpected serious adverse reaction (SUSAR) is any AE, AR or UAR that at any dose:

- results in death;
- is life threatening (i.e. the patient was at risk of death at the time of the event; it does not refer to an event which hypothetically might have caused death if it were more severe);
- requires hospitalisation or prolongation of existing hospitalisation;
- results in persistent or significant disability or incapacity;
- is a congenital anomaly or birth defect.

Note: Hospitalisations for treatment planned prior to randomisation and hospitalisation for elective treatment of a pre-existing condition will not be considered as an AE. Complications occurring during such hospitalisation will be AEs.

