12.3 Estimation of Sample Size

With the clinical safety data that are available we do not expect any adverse events but we note that PP100-01 has not been administered in paracetamol overdose patients treated with NAC. We deem that 6 patients per group in this initial dose escalation study will allow initial exploration of effects on biomarkers and potential dose limiting toxicity.

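### Within a dosing cohort, expected serious reactions related to PP100-01 or NAC have no automatic enrolment pause and no count threshold unless they end in death, critical care or a liver transplantation unit

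*Protocol*

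**What the plan says.** Protocol section 10.10, repeated in the synopsis, gives the rule: "All further patient enrolment will be paused pending advise from the SDMC if one of the following stopping rules have been met". The two triggers are:

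- "Patient death, admission to a Critical Care Unit or admission to a Liver Transplantation Unit due to any reason"
- "One SUSAR that definitely or probably relates to either PP100-01 or NAC or both"

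Section 10.2 defines an unexpected reaction as one that "is an adverse reaction that is not consistent with the product information in the IB/SoPC", and section 10.4.4 assesses expectedness against the same product information. Section 10.2 also makes an event serious if it "requires hospitalisation or prolongation of existing hospitalisation", so a reaction can be serious without coming near the first trigger.

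Other provisions bear on the point:

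- **Protocol 6.6.1:** 24 hours must pass after the first PP100-01 patient in each cohort is recruited, so that early adverse events can be seen.
- **Protocol 10.10:** the SDMC Chairperson receives information during recruitment that includes serious events attributed to treatment. The committee is to detect safety signals early, under a Charter that is not among the documents.
- **Synopsis:** the SDMC reviews safety between cohorts, before the next dose opens.
- **Protocol 12.3:** six patients per group "will allow initial exploration of effects on biomarkers and potential dose limiting toxicity".
- **Protocol 6.7:** dose limiting toxicity decides which patients are replaced. No section defines the term.
- **SAP 4.4 and 4.9:** relationship and expectedness are recorded separately for NAC and for PP100-01.

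**The concern.** The second trigger is the only one tied to drug causality, and it asks whether a reaction is new in kind. It does not ask whether a known reaction is becoming more frequent.

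For an add-on drug, more frequent known reactions are a plausible form of harm. Protocol section 13.1 says that the combination has not been studied in humans. The PP100-01 bolus comes directly after the NAC loading dose. On the timing of NAC anaphylactoid reactions, section 2.2.2 says "Thus they are most common during, or soon after, the initial high dose infusion" (this describes the older 20.25-hour regimen). For PP100-01 itself, section 2.3 states: "Immediate blood pressure fall, severe diarrhoea and severe vomiting, have previously been identified as important potential risks".

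At stake is whether a cluster of such reactions at a new dose must be looked at before all six patients have been dosed, or whether that is left to discretion. The arrangement fits poorly with the SDMC's task of early signal detection. It also fits poorly with a sample size justified by dose limiting toxicity, because that term has no link to the pause rule.

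**Working it through.** **The plan's own figures.** The pause rule states no probability, so there is none to reproduce. The sample size is a judgement without a formula; its arithmetic, 3 × (6 + 2) = 24, agrees.

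**Step 1: which serious related reactions pause enrolment?**

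| Serious related reaction | Trigger 1 | Trigger 2 | Mandatory pause |
|---|---|---|---|
| Ends in death, critical care or liver transplantation unit; expected or not | met | – | yes |
| Other outcome, unexpected, definitely or probably related | not met | met | yes |
| Other outcome, expected, any causality grade, any number | not met | not met | no |

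The third row is the gap. It follows from sections 10.2, 10.4.4 and 10.10 alone.

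**Step 2: how often would the gap matter?** Inputs:

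- n = 6 PP100-01 patients per cohort (Protocol 6.6.1).
- p = chance per patient of an expected serious related reaction. This is assumed; the documents give no rate. Section 2.2.2 reports about 15% anaphylactoid reactions, but that covers all severities on the older regimen, and section 3.2 says that the 12-hour regimen has fewer.
- q = share of those reactions that meet trigger 1. This is also assumed.

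Formulas:

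- P(at least one) = 1 − (1 − p)^6
- P(two or more) = 1 − (1 − p)^6 − 6p(1 − p)^5
- P(mandatory pause from these reactions, current rule) = 1 − (1 − pq)^6

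For p = 0.15: 1 − 0.85^6 = 1 − 0.377 = 0.623. For two or more: 0.623 − 6 × 0.15 × 0.85^5 = 0.623 − 0.399 = 0.224. With q = 0.10: 1 − 0.985^6 = 0.087.

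| p | At least one in 6 | Two or more in 6 | Pause, q = 0 | Pause, q = 0.10 | Pause, q = 0.50 |
|---|---|---|---|---|---|
| 0.05 | 26.5% | 3.3% | 0% | 3.0% | 14.1% |
| 0.15 | 62.3% | 22.4% | 0% | 8.7% | 37.4% |
| 0.30 | 88.2% | 58.0% | 0% | 16.7% | 62.3% |

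The 0% column restates the third row of step 1. It is built in by setting q = 0 and is not a separate result.

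**Step 3: what would closing the gap cost?** Take s as the background rate, per PP100-01 patient, of serious NAC-type reactions that would have happened anyway (assumed). Suppose, as a yardstick only, that one such reaction were enough for a pause. Over 3 × 6 = 18 PP100-01 patients, P(at least one extra pause) = 1 − (1 − s)^18.

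| s | Extra pause over the trial |
|---|---|
| 0.5% | 9% |
| 1% | 17% |
| 2% | 30% |
| 5% | 60% |

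**The case against.** A reader might infer that listed reactions can never pause a cohort, however many occur. The documents do not support that. Trigger 1 applies whatever the cause, so a listed reaction that ends in death, critical care or a liver transplantation unit does pause enrolment. A listed reaction whose nature or severity goes beyond the product information could also be classed as unexpected.

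A reader might also infer that any rash, wheeze or hypotension after the bolus would count as expected because NAC is known to cause it. SAP 4.4 and 4.9 record expectedness for each drug, so a NAC listing does not make a PP100-01 reaction expected. The gap therefore mainly concerns reactions attributed to NAC, and any PP100-01 reactions that the Brochure lists as expected. Section 2.3 calls its three items potential risks, and the Brochure is not available.

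Nor is it right that six patients are dosed before anyone can look. Section 6.6.1 imposes the 24-hour gap, which suits an acute bolus reaction. The synopsis has the SDMC consider an unexpected rise in severity. The Chairperson receives treatment-related serious events during recruitment, and section 16.5 lets the investigators terminate the study at any time. The Charter may hold further rules.

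All of that stands. None of these visible provisions, however, requires a pause for an expected serious related reaction within a cohort: the 24-hour gap names no consequence, the reports carry no stated frequency or threshold, and the cohort review comes after the six have been dosed.

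Finally, serious-reaction rates of 5% to 30% have no source in the documents, and section 2.3 reports no meaningful difference from placebo in the earlier calmangafodipir study. The tables are illustrations.

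**Conclusion.** The concern holds in limited form. A serious reaction that is related to PP100-01, NAC or both, is consistent with the product information and does not meet trigger 1 has no automatic pause and no count threshold within a cohort.

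At an assumed p of 0.15, about one PP100-01 group in five (22.4%) would have two or more serious related reactions of an expected kind. The current rule would pause for reactions of this kind with probability 8.7% to 37.4% if 10% to 50% of them met trigger 1, and 0% if none did.

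The existence of the gap rests on the wording alone; its size rests on assumed p and q. Confidence is medium, because the SDMC Charter, the Investigator's Brochure and the NAC product information could not be checked. This is a worthwhile, inexpensive improvement. It does not show that the study lacks safety oversight.

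**What to change.** The sponsor and the SDMC should reconcile the pause rule (synopsis and Protocol 10.10) with sections 6.6.1, 6.7 and 12.3 and with the Charter. Mandatory SDMC review of serious related reactions in PP100-01 patients within a cohort should not depend on whether the reaction is expected. The reconciled text should also:

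- define dose limiting toxicity and say whether it bears on the pause rule;
- say what follows if a serious reaction is seen in the 24-hour gap.

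The threshold and the causality grade are for the sponsor and the SDMC to set; this review proposes neither.

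The cost is an amendment to the two places that state the rule, with matching edits in the linked sections and the Charter. The existing committee and the existing 24-hour reporting of serious events would serve. The downside is the chance of an extra short pause for what proves to be ordinary NAC toxicity. Step 3 shows that this chance depends strongly on a background rate that the documents do not give, so it should be considered when the threshold is chosen.
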